8.2.2 Reporting serious adverse events

Serious AEs require immediate notification by the investigator or designee to QED Therapeutics Corporation beginning from the time the patient provides informed consent (ie, prior to undergoing any study-related procedure and/or receiving investigational product), through and including 30 days after the last administration of study treatment, or the investigator/patient decision to discontinue treatment, whichever occurs later. Any SAE occurring any time after the reporting period must be promptly reported to QED Therapeutics immediately after becoming aware of the SAE if a causal relationship to the investigational product is suspected. All SAEs ongoing 30 days or more after last dose of study drug is administered should be followed at least every 4 weeks until they resolve to baseline (or CTCAE grade ≤ 1), stabilize, or are considered to be chronic/irreversible. Should the FDA or national regulatory authorities require that the sponsor submit additional event data, the investigator will be asked to provide those data to the sponsor in a timely fashion.

8.2.2.1 Serious adverse event reporting period

The Ohio State University will be solely responsible for reporting serious adverse events to the OSU IRB, FDA, and QED Therapeutics. Participating subsites report directly to OSU and must report serious adverse events to the OSU PI and Multi-Site Coordinator within 24 hours of knowledge of the event. Serious adverse events are to be reported to the OSU IRB (per policy), FDA (per 21CFR312.32), and the appropriate monitor or subcommittee or task force within QED Therapeutics or its designated representative beginning from the time the patient is first administered investigational product through and including 30 days after permanent discontinuation of the investigational product. Any SAEs occurring any time after the reporting period must be promptly reported to the OSU IRB (per policy), FDA (per 21CFR312.32) and QED Therapeutics if a causal relationship to the investigational product is suspected.

Patients must be followed for all AEs from the date the patient is first administered investigational product until at least 30 Days after the End of Treatment, and for all serious or study drug-related toxicities until the AEs are resolved or until patient contact discontinues.

8.2.2.2 Immediate reporting of serious adverse events

NOTE: External participating sites are NOT permitted to report directly to the FDA or The Ohio State University Office of Responsible Research Practices (ORRP [OSU IRB]). All reports must be sent to the OSU Principal Investigator and Multi-Site Coordinator for review and submission to the FDA and ORRP. Sites must also report to their IRB according to their institutional guidelines.

The Investigator or designee must notify the OSU PI and Multi-Site Coordinator within 24 hours of knowledge of an SAE. OSU will then notify the OSU IRB (per policy), FDA (per 21CFR312.31) and QED Therapeutics Corporation. A complete SAE report using the FDA MedWatch 3500A Mandatory Reporting Form must be submitted to OSU within 3 business days. Additional or follow-up information on a SAE must also be reported immediately (ie, within 24 hours of new SAE information) and on the MedWatch 3500A form. Should the FDA, OSU IRB, or QED Therapeutics require additional data on the event, the Investigator will be asked to provide those data to OSU in a timely fashion.

All SAEs should be reported to the OSU IRB using the most current version of the Event Reporting Form (available at <http://go.osu.edu/Buck-IRB>) within 10 days of the Investigator's or research staff member's learning of the event (per IRB policy). Events resulting in temporary or permanent interruption of study activities by the Investigator or funding organization to avoid potential harm to participants should be reported immediately (within 48 hours) whenever possible. SAEs reported from participating institutions will be reported to the IRB by the Multi-Site Coordinator. Participating institutions are responsible for reporting to their local IRB per their institutional guidelines.

8.2.2.3 Information to be provided by the Investigator for a serious adverse event

SAEs are to be reported using the FDA MedWatch 3500A Mandatory Reporting Form. Information about the SAE that must be provided includes (refer to the SAE Cover Sheet in the Supplemental Forms packet):

- Investigator identification
- Patient identification (e.g., study assigned sequence ID)
- Information on study drug and concomitant therapies (e.g., start/stop date, dose and frequency of study drug)
- Description of event
- Severity of the SAE
- Relationship of the SAE to the study drug, the patient's disease, or other contributing factors
- Outcome of the SAE

8.2.2.4 Follow-up information on a serious adverse event

Appropriate diagnostic tests should be performed and therapeutic measures, as medically indicated, should be instituted. Appropriate consultation and follow-up evaluations should be carried out until the event has resolved or is otherwise explained by the Investigator. For all SAEs, the investigator is obligated to pursue and provide information to the OSU PI. In addition, an investigator may be requested by the OSU PI to obtain specific information in an expedited manner. This information may be more detailed than that captured on the SAE form. In general, this will include a description of the AE in sufficient detail to allow for a complete medical assessment of the case and independent determination of possible causality. Information on other possible causes such as concomitant medication and illnesses must be provided.

8.2.2.5 Required follow-up for serious adverse events

There should be routine follow-up for 30 days after permanent discontinuation of study drug in all patients in order to monitor for the occurrence of SAEs. If an SAE continues after the 30-day evaluation period,

then the patient must be followed until the event resolves or stabilizes. The medical monitor may specify a longer period of time, if required to assure the safety of the patient.

8.2.2.6 QED Therapeutics responsibility for expedited safety reports

QED Therapeutics will notify investigators of all reportable SAEs. This notification will be in the form of an expedited safety report. The OSU Multi-Site Coordinator will distribute safety reports to the external participating sites. Upon receiving such notices, the investigator must review and retain the notice with other study-related documentation. The OSU PI and Institutional Review Board (IRB) will determine if the informed consent requires revision. The investigator should also comply with the IRB procedures for reporting any other safety information. Suspected serious adverse reactions and other significant safety issues reported from the study shall be reported to the relevant competent health authorities in all concerned countries according to local regulations (either as expedited safety reports and/or in aggregate reports), by QED Therapeutics or its designated representative.

QED Therapeutics: All serious adverse events that are considered related or unrelated to Infigratinib treatment will be recorded on the SAE Report Form and sent within **24 hours** upon learning of the event to: Email: [contact]; [contact]

Exchange of safety information

a) From The Ohio State University to QED Therapeutics:

- Serious adverse events, as defined in FDA regulations 21 CFR 312.32 are to be reported to QED Therapeutics or QED Therapeutics's designee no later than at time of submission to the FDA per the time frames outlined in 21 CFR 312.32.
- Reports of all adverse events related to the study that have been submitted to the appropriate regulatory authorities in accordance with Applicable Law would be sent to QED Therapeutics within 24 hours after reporting including the submission documents.
- Reports of pregnancies in female subjects and female partners of male subjects and pregnancy outcomes will be promptly provided to QED Therapeutics.
- Study institution will promptly respond to QED Therapeutics queries on SAE and make available Medical Records or Study Data as QED Therapeutics may deem necessary to investigate and/or report on an adverse event.
- Reports of non-serious adverse events will be routinely collected during the trial in an appropriately configured database and provided to QED Therapeutics with dedicated outputs.

b) From QED Therapeutics to The Ohio State University:

- Investigator's Brochures and other reference safety information
- QED Therapeutics agrees to promptly notify Investigator in writing promptly of information that could affect the safety or medical care of current or former subjects, influence the conduct of the Study, or alter the IRB's approval.

c) From The Ohio State University to External Participating Sites:

- Investigator's Brochures and other reference safety information (e.g. safety reports)
- Serious adverse events
- Other non-serious, but notable toxicities

8.3 Pregnancy and other safety issues

Females of childbearing potential and fertile males will be informed as to the potential risk of conception while participating in this study and will be advised that they must use effective contraception during the dosing and for a period of at least 4 months thereafter. A pregnancy test will be performed on each pre-menopausal female of childbearing potential prior to the first dose of study drug. A negative pregnancy test must be documented prior to administration of study drug.

If a patient is confirmed pregnant during the trial, study drug administration must be discontinued immediately. Information regarding a pregnancy must be immediately forwarded to the OSU PI, who will report the information to QED Therapeutics.

The Investigator must immediately report follow-up information to QED Therapeutics regarding the course of the pregnancy, including perinatal and neonatal outcome, regardless of whether the patient has discontinued participation in the study. If the pregnancy results in the birth of a child, additional follow-up information may be requested. If the pregnancy results in spontaneous abortion or stillbirth, the event should be reported as an SAE. Pregnancy outcomes must be collected for the female partners of any males who took study drug in this study. Consent to report information regarding these pregnancy outcomes should be obtained from the female partner.

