 - a. Congestive heart failure requiring treatment (NYHA Grade \geq 2), LVEF $< 50\%$ as determined by MUGA scan or ECHO, or uncontrolled hypertension (refer to WHOISH guidelines)
 - b. History or presence of clinically significant ventricular arrhythmias, atrial fibrillation, resting bradycardia, or conduction abnormality
 - c. Unstable angina pectoris or acute myocardial infarction \leq 3 months prior to starting study drug
 - d. QTcF > 470 msec (males and females)
 - e. History of congenital long QT syndrome
19. Pregnant or nursing (lactating) women, where pregnancy is defined as the state of a female after conception and until the termination of gestation, confirmed by a positive hCG laboratory test.
20. Women of child-bearing potential (WOCBP), defined as all women physiologically capable of becoming pregnant, unless they are using highly effective methods of contraception during dosing and for 3 months following the discontinuation of study treatment. Highly effective contraception methods include:
 - a. Total abstinence (when this is in line with the preferred and usual lifestyle of the patient. Periodic abstinence (e.g., calendar, ovulation, symptothermal, post-ovulation methods) and withdrawal are not acceptable methods of contraception.
 - b. Female sterilization (have had surgical bilateral oophorectomy with or without hysterectomy) or tubal ligation at least six weeks before taking study treatment. In case of oophorectomy alone, only when the reproductive status of the woman has been confirmed by follow-up hormone level assessment.
 - c. Male sterilization (at least 6 months prior to screening). For female patients on the study the vasectomized male partner should be the sole partner for that patient.
 - d. Use of oral, injected or implanted hormonal methods of contraception or placement of an intrauterine device (IUD) or intrauterine systems (IUS), or other forms of hormonal contraception that have comparable efficacy (failure rate $< 1\%$), for example hormone vaginal ring or transdermal hormone contraception.

In case of use of oral contraception women should have been stable on the same pill for a minimum of 3 months before taking study treatment.

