Women are considered post-menopausal and not of child bearing potential if they have had 12 months of natural (spontaneous) amenorrhea with an appropriate clinical profile (e.g. age appropriate, history of vasomotor symptoms) or have had surgical bilateral oophorectomy (with or without hysterectomy) or tubal ligation at least 6 weeks ago. In the case of oophorectomy alone, only when the reproductive status of the woman has been confirmed by follow-up hormone level assessment is she considered not of child bearing potential.

21. Sexually active males unless they use a condom during intercourse while taking drug and for 3 months after the last dose of the study drug and should not father a child in this period. A condom is required to be used also by vasectomized men as well as during intercourse with a male partner in order to prevent delivery of the drug via seminal fluid.

6. Treatment

The investigational drug will be Infigratinib as an oral formulation.

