6.2 Dose modifications

6.2.1 Dose modifications and dose delay

For patients who do not tolerate the protocol-specified dosing schedule, dose adjustments are permitted in order to allow the patient to continue the study treatment. All dose modifications should be based on the worst preceding toxicity (**Table 6**). Dosage changes must be recorded on the Dosage Administration Record CRF.

The following guidelines should be applied.

Each patient will be allowed 3 dose reductions. Patients should discontinue Infigratinib if toxicities persist following 3 dose reductions (**Table 5**).

Following resolution of toxicity to baseline or \leq Grade 1, treatment is resumed at either the same or lower dose of study drug as per the criteria in **Table 6**. If treatment is resumed at the same dose of study drug, and the same toxicity recurs with the same or worse severity regardless of duration, dose must be reduced to the next lower dose level. If treatment is resumed at the lower dose of study drug, and the same toxicity recurs with the same or worse severity, the patient should have a second dose reduction.

Patients who discontinue the study for a study related adverse event or an abnormal laboratory value must be followed as described in Section 8.

In exceptional situations, study treatment may continue even if the patient experienced one of the treatment stopping rules. The decision to allow for continuation of treatment will be made on a case-by-case basis following discussion with the Principal Investigator (Sponsor).

Situations that may allow for continuation of treatment include the following:

- A dose delay of > 14 days has occurred, but the patient is clearly benefiting from study treatment (i.e., stable disease, partial response, or complete response) and it is the investigator's opinion that no safety concerns are present. If the patient is clearly benefiting from the study treatment (i.e. stable disease, partial response, or complete response), and in the opinion of the investigator no safety concerns are present, after discussion with QED Therapeutics Medical Monitor, the patient may remain on the study treatment.
- A third or subsequent reduction (to 50 mg) in dose may be allowed if the patient is clearly benefiting from study treatment (i.e., stable disease, partial response, or complete response) but is experiencing adverse events that prevent continued treatment at the already reduced dose.

Table 5: Dose reduction table

Dose reduction				

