11.3 Informed consent procedures

Eligible patients may only be included in the study after providing written (witnessed, where required by law or regulation), IRB/IEC/REB-approved informed consent.

Informed consent must be obtained before conducting any study-specific procedures (i.e. all of the procedures described in the protocol). The process of obtaining informed consent should be documented in the patient source documents. The date when a subject's Informed Consent was actually obtained will be captured in their CRFs.

OSU Investigator Team will provide to investigators, in a separate document, a proposed informed consent form (ICF) that is considered appropriate for this study and complies with the ICH GCP guideline and regulatory requirements. Any changes to this ICF suggested by the investigator must be agreed to by QED Therapeutics before submission to the IRB/IEC/REB, and a copy of the approved version must be provided to the QED Therapeutics monitor after IRB/IEC/REB approval.

Women of child bearing potential should be informed that taking the study medication may involve unknown risks to the fetus if pregnancy were to occur during the study and agree that in order to participate in the study they must adhere to the contraception requirement for the duration of the study. If there is any question that the patient will not reliably comply, they should not be entered in the study.

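### Three safety rules contradict themselves in the current text: how long contraception lasts after treatment, whether a third dose reduction is a standing allowance or an exception, and when SAE reporting to the industry partner begins

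*Combined protocol and SAP*

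**What the plan says.** **Contraception after treatment.** Criterion 20 in Section 5.3 excludes women of child-bearing potential "unless they are using highly effective methods of contraception during dosing and for 3 months following the discontinuation of study treatment". Criterion 21 excludes sexually active men "unless they use a condom during intercourse while taking drug and for 3 months after the last dose". Section 8.3 covers both sexes and has them advised that "they must use effective contraception during the dosing and for a period of at least 4 months thereafter". Section 11.3, on what women are told at consent, says only that "they must adhere to the contraception requirement for the duration of the study".

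**Dose reductions.** Section 6.2.1 states a general rule: "Each patient will be allowed 3 dose reductions". It pairs this with a stopping point: "Patients should discontinue Infigratinib if toxicities persist following 3 dose reductions". Later in the same section comes a list of exceptional situations in which a patient who has met a stopping rule may stay on drug after case-by-case discussion. One entry reads: "A third or subsequent reduction (to 50 mg) in dose may be allowed if the patient is clearly benefiting from study treatment". Table 5 lists three levels below the starting dose (100, 75 and 50 mg) and attaches no condition to the lowest. The note closing Table 6 says that patients needing more than two reductions will in general come off study drug. It also permits re-escalation case by case.

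**Start of SAE reporting.** Section 8.2.2 has the investigator notify the industry partner of SAEs from informed consent onward. Section 8.2.2.1 has the lead site report SAEs to its IRB, the FDA and the same partner from first dose onward. Sections 8.2.2.2 and 8.2.2.6 also require onward reporting but give no start date.

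**The concern.** Sites apply these rules patient by patient, and each rule has two incompatible statements. Section 12 allows no authorised deviations and Section 12.1 requires a written amendment for any change, so a site cannot settle the matter itself.

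- **Contraception:** a patient who commits to exactly 3 months is eligible under criterion 20 or 21 and still falls short of Section 8.3.
- **Dose:** a patient who has had two reductions and needs another can be reduced again at one site and discontinued at another. That choice feeds the summaries of reductions and dose intensity (Table 3 and Section 10.3) and the tabulation of events resulting in treatment discontinuation (Section 10.5).
- **SAEs:** an event between consent and first dose is inside the partner's reporting period in Section 8.2.2 and outside it in Section 8.2.2.1. One possible source is a new tumor sample taken at screening because no archival sample exists (Section 7.2.3.1).

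**Working it through.** The check is mainly a comparison of passages; the only arithmetic is one subtraction.

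**1. Contraception**

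| Place | Who | Period after treatment |
|---|---|---|
| Criterion 20 | Women of child-bearing potential | 3 months |
| Criterion 21 | Sexually active men | 3 months |
| Section 8.3 | Both | at least 4 months |
| Section 11.3 | Women, at consent | no figure |

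Gap = 4 − 3 = 1 month. It is a minimum because Section 8.3 sets a floor. The conflict runs one way: 4 months satisfies a 3-month duration, but 3 months does not satisfy a 4-month floor. This concerns duration only, since the passages also describe the required method differently. Section 11.3 ties the requirement to the length of the study and gives no period after dosing, so it cannot decide between 3 and 4.

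**2. Third dose reduction**

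Take a patient who has had two reductions (125 to 100 to 75 mg, with no re-escalation) and again needs a lower dose.

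- General rule in 6.2.1: the third reduction is within the allowance. Discontinuation follows only if toxicity persists after it.
- Exception list in 6.2.1 with the Table 6 note: the general course is discontinuation. A third reduction to 50 mg needs clear benefit and a case-by-case decision.

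These give two different defaults for one patient. Table 5 shows that a third level exists but not on what terms. The Table 6 note does not say whether a re-escalated dose resets the count, so the limit is unclear for such patients too.

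**3. Start of SAE reporting**

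| Place | Activity | Start |
|---|---|---|
| 8.2.2 | Investigator to industry partner | consent |
| 8.2.2.1 | Lead site to IRB, FDA and industry partner | first dose |
| 8.2.2.2 | Lead site to IRB, FDA and industry partner | not given |
| 8.2.2.6 | SAEs to industry partner | not given |
| 7.1.2.2 | Screening SAEs in screen failures entered in the database | before first dose |
| 8.1.4 | AEs recorded on the eCRF | consent |
| 8.1.1 | Definition of an AE | tied to dosing |

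The partner is the only recipient given two different start points. For the IRB and FDA, only 8.2.2.1 states one. Sections 7.1.2.2 and 8.1.4 expect capture before first dose. Section 8.1.1 points the other way: it defines an AE in a subject given a product, and counts worsening of an existing condition from first dose.

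**The case against.** The strongest reply is that these are differences of wording that careful sites can live with.

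- **Contraception:** the criteria govern entry and Section 8.3 governs advice, and a patient who follows the longer period meets both durations. That is true, but it works only if every site reads past the criteria. The consent form, which might settle the matter, is a separate document not available here.
- **Dose:** the exception list and the Table 6 note fit together as one rule, a default of stopping with an override. That stands. A reader might infer that the protocol gives three different answers on the third reduction; it gives two. The combined rule still cannot be squared with a standing allowance of three for each patient.
- **SAEs:** Section 8.2.2 addresses the investigator and Section 8.2.2.1 the lead site, and sites must in any case tell the lead site within 24 hours of knowing of an event. That narrows the practical effect, but both sections name the same partner with different starts. A reader might also infer that Section 8.2.2.1 is a lone outlier. It is not, because the AE definition in Section 8.1.1 is tied to dosing as well.

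Several attempts to put a size on the problem also go beyond the text:

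- Capping the SAE window at 28 days per patient from Table 7 fails. Section 7.1.2 requires only that consent precede study-specific procedures and that out-of-window assessments be repeated, so the interval from consent to first dose can be longer.
- Counting one patient as 1/10 = 10 points or 1/30 = 3.3 points of a cohort assumes the grouping in Section 10. The Protocol Summary instead groups fusions against other alterations, which would give 1/(30 + 10) = 2.5 points for fusion patients.
- The tolerability measure in Section 7.2.2 counts delays together with discontinuations. A patient held before a reduction would usually count either way.
- Placing the third reduction at a level other than 75 to 50 mg requires re-escalation and a counting rule that the protocol does not supply.

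**Conclusion.** The point holds. Three safety rules are each stated in two incompatible ways in the current text, and no precedence rule decides between them. The contraception gap is at least 1 month, taking the 3- and 4-month periods to run from the same end of dosing. The dose conflict is two-way: a standing allowance of three reductions, against general discontinuation beyond two with a third by exception. The direct SAE conflict is confined to reporting to the industry partner for events between consent and first dose.

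The last two cannot be sized, because the documents give neither the number of patients expected to reach a third reduction nor the number of SAEs expected before first dose. The effect on analysis is limited to the reduction and dose-intensity summaries and the tabulation of events resulting in discontinuation. A reader might infer that the trial's statistical conclusions are at risk; the documents do not support that, since neither the sample size nor the Cohort 1 decision rule depends on these passages. The reason to act is consistent patient counselling, dosing and safety reporting across sites.

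**What to change.** In one amendment, reconcile the passages so that each rule is stated once and identically:

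- **Contraception duration:** criteria 20 and 21 in Section 5.3, Section 8.3, and the consent wording under Section 11.3.
- **Number of dose reductions and any conditions on them:** both places in Section 6.2.1, Table 5 and the note closing Table 6, including how a re-escalated dose is counted.
- **AE and SAE start point:** Sections 7.1.2.2, 8.1.1, 8.1.4, 8.2.2, 8.2.2.1, 8.2.2.2 and 8.2.2.6.

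Which duration, reduction limit, conditions and start point apply is for the sponsor to decide; this review takes no position. The cost is protocol wording in a single amendment and a check that the consent form matches. No procedures are added.
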